6. STUDY DESIGN AND STATISTICAL CONSIDERATIONS

6.1 Study Design and Endpoints

This is a single-arm, pilot trial in patients with metastatic high grade large cell neuroendocrine carcinoma (HG-LCNEC) to study the feasibility of upfront NGS directed treatment in high grade neuroendocrine carcinomas. Tumor samples will receive next generation sequencing (NGS) profiling to classify the tumor as: small cell-like or non-small cell-like. Non-typeable cases will not be eligible for participation in this study, neither is small cell neuroendocrine carcinoma (HG-SCNEC). The systemic therapy regimen will be determined based on the NGS profile of the tumor.

Feasibility is defined as being able to sequence the patient within 2 months of initial medical oncology visit and being able to assign into molecularly-defined cohorts (TP53 and RB1 co-mutated vs non-co-mutated).

Secondary outcomes include ORR and progression-free survival (PFS). Radiological response will be assessed via RECIST Version 1.1 criteria (Appendix B) based on standard-of-care CT scans completed at q2 monthly intervals during treatment and q3 month during observation. PFS is defined from date of on study to the date of disease progression or death or date of last follow-up whichever occurs first. PFS will be assessed via standard-of-care CT scans (q2 month intervals during active treatment and q3 months during observation) as graded by RECIST Version 1.1 criteria for up to one year post-study enrollment.

All patients who received anticancer therapy will be included in the toxicity and safety analysis. Incidence tables will be generated to summarize incidence of patients reporting at least one episode of each specific AE, the incidence of AE causing withdrawal from the study and incidence of SAE. The total number of episodes for each event reported (Frequency Table), the severity and attribution to study therapy of each episode reported (Severity Table and Attribution Table) will also be evaluated.

Listings of AEs by patients will include the following information: time to onset, the duration of each AE, the severity of each AE, the relationship of the AE to study therapy, whether it was a serious AE (or not), and whether the AE caused withdrawal. Toxicities will be graded according to Common Toxicity Criteria (CTCAE) v5.

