- *Research Repositories*: If the purpose of this submission is to establish a Research Repository (bank, registry) and the material you plan to collect is already available from a commercial supplier, clinical lab, or established IRB approved research repository, provide scientific justification for establishing an additional repository collecting duplicate material. Describe the repository design and operating procedures. For relevant information to include, see the [UK Research Biospecimen Bank Guidance](#) or the [UK Research Registry Guidance](#).

This is a single-arm, pilot trial in patients with metastatic high grade large cell neuroendocrine carcinoma (HG-LCNEC) to study the feasibility of upfront NGS directed treatment in high grade neuroendocrine carcinomas. Tumor samples will receive next generation sequencing (NGS) profiling to classify the tumor as one of three subtypes: small cell-like, non-small cell-like or non-typeable. Non-typeable cases will not be eligible for participation in this study, neither is small cell neuroendocrine carcinoma (HG-SCNEC). The systemic therapy regimen will be determined based on the NGS profile of the tumor.

Feasibility is defined as being able to sequence the patient within 2 months of initial medical oncology visit and being able to assign into molecularly-defined cohorts (TP53 and RB1 co-mutated vs non-co-mutated).

Secondary outcomes include ORR and progression-free survival (PFS). Radiological response will be assessed via RECIST Version 1.1 criteria (Appendix B) based on standard-of-care CT scans completed at q2 monthly intervals during treatment and q3 month during observation. PFS is defined from date of on study to the date of disease progression or death or date of last follow-up whichever occurs first. PFS will be assessed via standard-of-care CT scans (q2 month intervals during active treatment and q3 months during observation) as graded by RECIST Version 1.1 criteria for up to three years post-study enrollment.

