6.2 Sample Size/Accrual Rate

We plan to enroll 15 patients on this pilot trial to study the feasibility of upfront NGS directed treatment in high grade neuroendocrine carcinomas and evaluate the ORR and progression-free survival.

Feasibility is defined as being able to sequence the patient within 2 months of initial medical oncology visit and being able to assign into molecularly defined cohorts (TP53 and RB1 co-mutated vs non co-mutated). If more than 50% patients are not able to sequence within 2 months

of initial medical oncology visit or more than 50% patients are not able to assign into molecularly defined cohorts, the study will be deemed not feasible. No stopping rule is planned to stop enrollment based on feasibility. With 15 patients, the probability of unfeasible of the study is calculated with true unfeasibility probability p from 0.2 to 0.8 (Table 1). From this calculation we see if the true unfeasibility rate <0.5 , the probability to declaim the trial unfeasible is low and if the true unfeasibility rate >0.5 , the probability to declaim the trial unfeasible is high.

Table 1: Probability of unfeasibility for this pilot study

True prob. of unfeasible	$p=0.2$	$p=0.3$	$p=0.4$	$p=0.5$	$p=0.6$	$p=0.7$	$p=0.8$
Prob. of unfeasible	0.0042	0.050	0.213	0.50	0.787	0.950	0.996

The expected accrual rate is about 8 patients per year and accrual duration is approximately 2 years, with an additional 1 year follow-up after the last patient is enrolled on the study for observation of disease progression. Thus, the total study duration is about 3 years.

All patients who completed at least 2-cycle treatments will be evaluable for the ORR objective. Patients who fail to complete 2-cycles of the treatment due to toxicity or withdrawal from study will be excluded from the ORR evaluation. All patients enrolled on the study will be evaluable for the PFS.

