6.4 Analysis of Primary and Secondary Endpoints

Percentage of patients who are able to sequence within 2 months of initial medical oncology visit will be estimated and percentage of patients who are able to assign into molecularly defined cohorts will be estimated for assessment of feasibility of the study. The ORR will be estimated with a standard error (SE). All patients will be followed until disease progression, death or end of study, whichever occurs first, for evaluation of PFS. The PFS will be estimated using Kaplan-Meier method for the entire cohort. Summary statistics will be provided for the analysis of potentially targetable mutations in high grade neuroendocrine carcinoma.

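### PFS without an event runs to an undefined last follow-up rather than the last tumour assessment, so the Kaplan-Meier curve is too high if contact outlasts CT scanning

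*Combined protocol and SAP*

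**What the plan says.** Section 6.1 gives the rule: "PFS is defined from date of on study to the date of disease progression or death or date of last follow-up whichever occurs first". The same sentence stands under Study Design in the Research Description of the IRB application. Both texts then tie PFS to imaging. In 6.1 the words are "PFS will be assessed via standard-of-care CT scans (q2 month intervals during active treatment and q3 months during observation", and the sentence ends "as graded by RECIST Version 1.1 criteria for up to one year post-study enrollment". The IRB application ends the same sentence "as graded by RECIST Version 1.1 criteria for up to three years post-study enrollment".

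Section 6.4 sets the length of follow-up: "All patients will be followed until disease progression, death or end of study, whichever occurs first, for evaluation of PFS". It names the estimator: "The PFS will be estimated using Kaplan-Meier method for the entire cohort". Section 6.2 sets the analysis set: "All patients enrolled on the study will be evaluable for the PFS". It also plans 15 patients at about 8 per year, one further year of follow-up after the last enrolment, and a study of about three years.

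The supplied text does not define last follow-up, link it to the last evaluable scan, or say how missed scans are handled.

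**The concern.** PFS has two components, RECIST progression and death, and they are observed differently. A death can be learned of at any contact. RECIST progression can be learned of only from a scan. After a patient's last scan, one component of the endpoint is invisible. If the patient stays in the risk set through that period, the denominator includes people whose progression could not have been recorded, and the estimated curve falls too slowly.

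On schedule the unscanned stretch is short, at most about three months. It grows if standard-of-care imaging lapses while clinic contact goes on, or if scanning stops at a fixed horizon and follow-up does not. The tail of the curve, where few of the 15 patients remain, is the most exposed. PFS is a named secondary objective.

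**Working it through.** **The plan's own figures.** The documents state no PFS figure, so there is none to reproduce. Table 1 in section 6.2 concerns feasibility only; its seven values reproduce as the exact binomial probability of 8 or more of 15.

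**Inputs from the documents.** N = 15; 8 patients per year; 12 months of follow-up after the last enrolment; CT every 2 months on treatment and every 3 months in observation; CT horizon of one year (6.1) or three years (IRB application).

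**Longest possible unscanned time.**
- Accrual: 15 / 8 × 12 = 22.5 months.
- First entry to end of study: 22.5 + 12 = 34.5 months.
- If CT stops at 12 months and follow-up runs to end of study: 34.5 − 12 = 22.5 months for the first patient.
- If CT runs for three years: 36 > 34.5, so the horizon itself creates no gap.

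**Assumptions, not in the documents.** Median PFS 6 months (range 4 to 9). In the runs with deaths, median 6 months from progression to death. Dropout or stopping of scans is varied. The true 18-month value at a 6-month median is 0.5^(18/6) = 12.5%; at 24 months it is 0.5^(24/6) = 6.2%.

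**Case 1: CT stops at 12 months, contact continues to end of study, deaths modelled.**

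| Time | Censored at last follow-up | Censored at last scan | Reference |
|---|---|---|---|
| 18 months | 20.0% | 12.9% | 12.5% (true) |
| 18 months, repeat run, just after the visit | 20.8% | 12.8% | 12.4% (full scanning) |
| 24 months | 13.5% | 4.3% | 6.2% (true) |

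The upward error at 18 months is 20.0 − 12.5 = 7.5 points, or 20.8 − 12.4 = 8.4 in the repeat. The direction is the same for medians of 4 to 9 months. With no deaths modelled and 20% per year stopping scans, the 18-month values are 0.330, 0.167 and 0.154 (full scanning). The error is then 0.330 − 0.154 = 0.176, so deaths seen in the unscanned period reduce the bias but do not remove it.

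**Case 2: CT horizon not limiting, but individual patients stop scans while contact continues (no deaths modelled).** At a 6-month median with 20% per year stopping scans, 12-month PFS by last follow-up, last scan and full scanning is:
- six further months of contact: 0.347 / 0.292 / 0.305, error 0.347 − 0.305 = +0.042;
- contact to end of study: 0.366 / 0.291 / 0.302, error 0.366 − 0.302 = +0.064.

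Over medians of 4 to 9 months and 10 to 40% per year stopping scans, the error runs from +0.016 to +0.104 with six further months of contact, and from +0.026 to +0.150 with contact to end of study.

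**Case 3: scanning continues and last contact precedes the next due scan.** The 12-month error of last-follow-up censoring is −0.010 to +0.004, which is simulation noise. With deaths modelled and 6% per month dropout, last-follow-up censoring gave 25.2% just after the 12-month visit against 25.0% with full scanning.

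**The alternative rule has its own error.** In Case 3, last-scan censoring reads low:
- without deaths, scans ±0.5 month, 20% per year stopping: 0.308 − 0.296 = 0.012, about 1 point;
- with deaths and 6% per month dropout: about 3 points at 12 months, and 14.8 − 11.5 = 3.3 points at 18 months.

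Part of the reason is that deaths between scans count as events while survivors are censored back to their last scan. Beyond the end of scanning it can read lower still: 4.3% against 6.2% at 24 months in Case 1, and 8.6% against 12.5% at 18 months when 6% per month dropout is added.

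**The case against.** A reader might infer that the curve will certainly be too high, or that the first patient will be credited with 22.5 unscanned months. The documents do not support either as a certainty.

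- The large figures need scanning to stop at 12 months while PFS follow-up runs on. The IRB application gives three years of assessment, which covers the whole 34.5 months. The one-year sentence in 6.1 can also be read as ending PFS assessment altogether at one year, and then nothing later is credited. The conflict between horizons is a separate defect, and its effect should not all be charged to the censoring sentence. This stands.
- With scanning maintained, last-follow-up censoring is about right and last-scan censoring is the rule that reads low. This stands too.
- A reader might take last follow-up to mean any contact. No text says so, and 6.4 describes follow-up as being for evaluation of PFS, which fits the last disease assessment equally well. A reader might also infer that last follow-up counts as an event because it is listed beside progression and death. Kaplan-Meier estimation in 6.4 makes censoring the natural reading.
- The practical effect is modest. In simulated 15-patient trials (median 6 months, 3% per month dropout) the Kaplan-Meier median was identical under the two rules in 84 to 86%. The standard deviation of the 18-month estimate was 12 to 13 points, larger than the 7.5-point shift, which is about one patient (1/15 = 6.7 points).
- The study calendar and the RECIST appendix are not in the supplied text, so a rule there cannot be excluded.

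These points limit the claim but do not remove it. The endpoint sentence states a rule, and that rule gives an upward error whenever contact outlasts imaging. Because all scans are standard of care, lapses are plausible.

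**Conclusion.** The concern holds conditionally. Ending event-free PFS at an undefined last follow-up overstates PFS if contact outlasts scanning, and has almost no effect otherwise. If the one-year CT limit in 6.1 is combined with the follow-up to end of study in 6.4, 18-month PFS is about 20% against a true 12 to 13%. That figure rests on an assumed median PFS of 6 months and an assumed median of 6 months from progression to death. If scanning continues and last contact precedes the next due scan, the bias is near zero. The actual size depends on median PFS, dropout and which horizon applies, none of which the documents settle. PFS is a secondary, descriptive endpoint in 15 patients with no decision threshold, and the feasibility conclusion does not depend on it. The change is still worth making, because the ambiguity sits in the endpoint definition and is cheap to remove before analysis.

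**What to change.** In section 6.1 and in the Study Design text of the IRB application, replace the definition with: *PFS is the time from the on-study date to first RECIST progression or death; patients without an event are censored at their last adequate RECIST assessment.*

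In addition:
- Reconcile the one-year and three-year assessment horizons, so that scanning and PFS follow-up have a consistent stated end.
- Show the Kaplan-Meier curve only up to the last scheduled scan.
- Report last-follow-up censoring as a sensitivity analysis. Agreement between the two curves would show that contact did not materially outlast scanning.

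The cost is one sentence in two places and one extra curve. No visit or scan is added, and scan dates are needed for RECIST grading anyway. The statistical price should be stated in the plan: last-scan censoring can read about 1 to 3 points low when scans continue with dropout, and lower still beyond the end of scanning. The primary curve will therefore be slightly conservative.

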6.2 Sample Size/Accrual Rate

We plan to enroll 15 patients on this pilot trial to study the feasibility of upfront NGS directed treatment in high grade neuroendocrine carcinomas and evaluate the ORR and progression-free survival.

Feasibility is defined as being able to sequence the patient within 2 months of initial medical oncology visit and being able to assign into molecularly defined cohorts (TP53 and RB1 co-mutated vs non co-mutated). If more than 50% patients are not able to sequence within 2 months

of initial medical oncology visit or more than 50% patients are not able to assign into molecularly defined cohorts, the study will be deemed not feasible. No stopping rule is planned to stop enrollment based on feasibility. With 15 patients, the probability of unfeasible of the study is calculated with true unfeasibility probability p from 0.2 to 0.8 (Table 1). From this calculation we see if the true unfeasibility rate <0.5 , the probability to declaim the trial unfeasible is low and if the true unfeasibility rate >0.5 , the probability to declaim the trial unfeasible is high.

Table 1: Probability of unfeasibility for this pilot study

True prob. of unfeasible	$p=0.2$	$p=0.3$	$p=0.4$	$p=0.5$	$p=0.6$	$p=0.7$	$p=0.8$
Prob. of unfeasible	0.0042	0.050	0.213	0.50	0.787	0.950	0.996

The expected accrual rate is about 8 patients per year and accrual duration is approximately 2 years, with an additional 1 year follow-up after the last patient is enrolled on the study for observation of disease progression. Thus, the total study duration is about 3 years.

All patients who completed at least 2-cycle treatments will be evaluable for the ORR objective. Patients who fail to complete 2-cycles of the treatment due to toxicity or withdrawal from study will be excluded from the ORR evaluation. All patients enrolled on the study will be evaluable for the PFS.

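### ORR is restricted to patients who complete two cycles while PFS uses everyone enrolled, so the response set is selected after enrolment; early progression and death are not named, and only an SE is planned

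*Combined protocol and SAP*

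**What the plan says.** Section 6.2 sets the analysis populations in three consecutive sentences.

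- ORR set: "All patients who completed at least 2-cycle treatments will be evaluable for the ORR objective".
- ORR exclusions: "Patients who fail to complete 2-cycles of the treatment due to toxicity or withdrawal from study will be excluded from the ORR evaluation".
- PFS set: "All patients enrolled on the study will be evaluable for the PFS".

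Section 6.4 says that ORR will be reported with a standard error. It names no confidence interval and no interval method. The same section sets follow-up: "All patients will be followed until disease progression, death or end of study, whichever occurs first, for evaluation of PFS". Section 6.1 bases response on "standard-of-care CT scans completed at q2 monthly intervals during treatment and q3 month during observation", graded by RECIST 1.1, and defines the safety set separately: "All patients who received anticancer therapy will be included in the toxicity and safety analysis".

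The supplied text contains no ORR over all enrolled or all treated patients, no ORR sensitivity analysis, and no rule for patients without a response assessment.

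**The concern.** Completing two cycles is known only after enrolment and depends on how the patient fares. An ORR restricted to completers describes a subset selected by early outcome. It is too high if early stoppers respond less often than completers, unchanged if they respond equally often, and too low if they respond more often. The last case is possible: a patient who stops early for toxicity is still followed and scanned, and the rule would discard a response documented that way.

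The two ORR sentences also leave a gap. A patient who progresses or dies before two cycles is not evaluable under the first sentence, yet is not among the exclusions listed in the second. Two analysts could treat that patient differently, and in an open single-arm trial the choice would be made with the data in view. Such patients are foreseeable: the Background calls these tumours highly aggressive, and criterion 3.1.6 allows for patients in visceral crisis.

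ORR is one of two secondary outcomes. As written, it and PFS describe different groups of patients. A standard error alone is also a weak statement of uncertainty in 15 patients or fewer.

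**Working it through.** **Inputs from the documents.** 15 patients are enrolled in a single arm; the ORR and PFS sets are as in section 6.2; precision is the SE only (section 6.4). The sole operating characteristic given is Table 1, for feasibility. It reproduces as P(X ≥ 8) for X ~ Binomial(15, p): 0.0042, 0.050, 0.213, 0.50, 0.787, 0.950 and 0.996 for p = 0.2 to 0.8. Nothing comparable is given for ORR.

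**Assumed inputs.** The number k excluded, the number of responders, and how many of the excluded responded. None of these is in the documents.

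**Step 1: bias identity.** Let pc be the ORR in the 15 − k completers and ps the ORR in the k early stoppers.

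- Two-cycle ORR = pc
- All-enrolled ORR = [(15 − k)·pc + k·ps] / 15
- Difference = (k/15)·(pc − ps)

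If ps = 0, the two-cycle ORR is the all-enrolled ORR times 15/(15 − k): 1.07 at k = 1, 1.15 at k = 2, 1.25 at k = 3.

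**Step 2: direction.** Take 5 responders among 15 (33.3%) and k = 3.

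| Responders among the 3 excluded | Two-cycle ORR | Difference from 33.3% |
|---|---|---|
| 0 | 5/12 = 41.7% | +8.3 points |
| 1 | 4/12 = 33.3% | 0 |
| 2 | 3/12 = 25.0% | −8.3 points |

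The break-even count is 5 × 3/15 = 1 responder among the excluded.

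**Step 3: early progression or death.** Take 5 responders, all completers, 2 stops for toxicity or withdrawal, and 1 early progression or death.

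- That patient kept in the denominator: 5/13 = 38.5%
- That patient dropped: 5/12 = 41.7%
- All enrolled: 5/15 = 33.3%

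**Step 4: precision.** SE = √[p(1 − p)/n].

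- 0/15: SE = 0; exact (Clopper-Pearson) 95% upper limit 21.8%, Wilson 20.4%.
- 5/15: SE = 12.2 points; exact 95% CI 11.8% to 61.6%.
- 5/12: SE = 14.2 points; exact 95% CI 15.2% to 72.3%.

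The plan does not propose ORR ± 1.96 SE, but a reader given only an SE may form it. Actual coverage of the nominal 95% interval at n = 15:

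| True ORR | ± 1.96 SE | Clopper-Pearson | Wilson |
|---|---|---|---|
| 10% | 79% | 99% | 94% |
| 20% | 81% | 98% | 98% |
| 30% | 95% | 98% | 91% |
| 40% | 94% | 99% | 94% |
| 50% | 88% | 96% | 96% |

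The zero-SE case matters mainly at low response rates: P(0 of 15) = 0.9^15 = 0.206 at a true ORR of 10%, and 0.8^15 = 0.035 at 20%.

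**The case against.** **Small consequence.** ORR is a descriptive secondary outcome of a 15-patient feasibility pilot. The rule is stated in advance, and no joint analysis of ORR and PFS is planned. This stands, and it limits the weight of the point. It does not remove it: section 6.2 gives evaluating ORR as one reason for enrolling the 15 patients, and at this size each exclusion moves the estimate visibly.

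**Unknown magnitude.** Criterion 3.1.6 and Research Procedures allow up to two cycles before enrolment or while sequencing is pending. If those cycles count toward the two, k could be 0 or 1 and the effect small. That is fair, and it is a reason to say which cycles count.

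**Early progression and death.** The first ORR sentence, read literally, already leaves these patients out. Part of this gap is therefore drafting, but the literal reading is also the one that removes likely non-responders.

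**Scan timing.** With scans every two months, many patients who stop early may have no on-treatment scan, so the downward scenario is less likely than the upward one. The documents do not give cycle length and cannot settle this.

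**Interval choice.** The SE-based interval covers well at a true ORR of 30% to 40%, and at 30% it does better than Wilson. The case for an interval rests on low and mid-range rates and on the zero-responder result.

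**Limits of an all-enrolled ORR.** The listed eligibility criteria do not require measurable disease, and an all-enrolled ORR can mix failure to assign with failure of treatment. Both are reasons to write the definition carefully, not to keep a completers-only ORR as the sole estimate.

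**Conclusion.** The concern holds. As written, the plan yields one ORR, in a set selected on early treatment course and different from the PFS set. It leaves early progression and death to inference and gives a precision measure that fails when there are no responders.

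The direction of the distortion is not fixed. It is upward if early stoppers respond less often than completers. In the illustration of 5 responders with 3 of 15 excluded, it runs from +8.3 to −8.3 points as the number of responders among those excluded goes from none to two. These counts are assumptions. Only how ORR is read is affected: it has no target or decision rule.

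**What to change.** In sections 6.2 and 6.4:

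1. Define the main ORR as responders divided by all enrolled patients, the same set as PFS. Count anyone without a documented RECIST 1.1 response as a non-responder, including after early toxicity, withdrawal, progression or death.
2. Report it with an exact (Clopper-Pearson) or Wilson 95% confidence interval.
3. Keep the two-cycle ORR as a labelled sensitivity analysis, and state in words how early progression and death are handled in it.
4. If some enrolled patients never start assigned therapy, also report ORR in all treated patients, matching the safety set in section 6.1. Section 6.2 allows for this case ("more than 50% patients are not able to assign into molecularly defined cohorts"), although section 6.1 makes non-typeable cases ineligible, so the text should say who counts as enrolled.
5. Unless protocol sections not supplied already do so, state whether cycles given before enrolment or during sequencing count toward the two, and how patients without measurable disease are classified.

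The cost is a few sentences. No patients or scans are added, because all patients are already followed for PFS. The reported ORR may be lower, and it will be less comparable with reports that use an evaluable set; the retained sensitivity analysis covers that comparison.
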